3.1 Summary

Data are entered remotely via electronic Case Report Form (eCRF) within an Electronic Data Capture (EDC) system. The database is designed and validated by the data manager to ensure accuracy. Only authorized site staff may enter or edit data, with each entry logged by a unique user ID and confirmed by electronic signature. All corrections are traceable (cross-out notation, reason, signature, date) without erasing original records, and a full audit trail is maintained. Unless specified, eCRF is not a source document; monitors verify its consistency with source data.

3.2 Data management

Data management includes logic checks, queries for inconsistent/missing data, and ongoing quality control. Treatment-emergent adverse events and concomitant medications are coded.

3.3 Data Verification

Data verification includes logical, manual, medical, and statistical checks. Queries are issued via the EDC system and resolved by the investigator/CRC until all data are validated. Upon data entry, the database will validate data in real time based on pre-programmed validation rules. Each participating center will have a data manager who verifies the completeness, consistency, and timeliness of all data. For missing data, the data manager is also responsible for retrieving the original data, with a high likelihood of successful retrieval.

3.4 Database Lock

After all source data are entered and reviewed by the Principal Investigator, statistician, and data manager with no unresolved queries, the database lock form is signed, and the database is locked. Locked data are exported for statistical analysis and cannot be edited. Minor post-lock discrepancies are corrected and documented in the statistical program.

4. Data Analysis

4.1 Timing of Analysis

The final statistical analysis will be performed after database lock, which will occur after all patients have completed the 90-day follow-up and all data have been verified, cleaned, and resolved with no outstanding queries. There were no planned interim analyses for the primary outcome in this trial.

4.2 General calculations

For the summary of population characteristics, all percentages will be calculated with the total number of the intent-to-treat (ITT) population as the denominator (including all patients with missing data for the relevant variable). For the summary of categorical outcome variables (e.g., complication rate), patients with missing data will be excluded from the denominator when calculating percentages. For the summary of continuous outcome variables (e.g., estimated blood loss, length of hospital stay, cost), patients with missing data will be excluded when calculating means or medians. When patients with missing data are excluded from the denominator, the number of patients included in the summary will be clearly reported.

All percentages, means, standard deviations (SDs), medians, interquartile ranges (IQRs), and ranges will be rounded to 2 decimal place. P-values will be rounded to 3 decimal places. Parameter estimates, standard errors (SEs), relative ratios (RRs), and 95% confidence intervals (CIs) will be reported to 2 decimal places. The primary outcome will be performed one-sided at $\alpha = 0.025$, with results presented as treatment differences and corresponding 97.5% one-sided confidence intervals. Other comparisons will be two-sided at $\alpha = 0.05$, with 95% two-sided confidence intervals reported.

4.3 Missing data

For missing baseline data (age, BMI, etc.), multiple imputation by chained equations (MICE) will be used. The number of imputed datasets, imputation variables, and diagnostic checks will be fully documented. For quality of life (QoL) data with missing values, only observed cases will be included in the analysis (missing values excluded from denominator). For crossover or treatment-switching patients, the ITT principle will be strictly maintained in the primary analysis; treatment switching will be summarized descriptively and explored in the as-treated sensitivity analysis. For protocol deviations, all major violations will be listed by center and patient, with impact on the primary outcome assessed in PP and AT analyses.

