Statistical Analysis Plan (Final, Version 1.2)

Principal Investigator: [name]

Research Institution: Sir Run Run Shaw Hospital, Zhejiang University

Register Number: NCT06204497

Date: 2025-10-26

Version: 1.2

Statistical Analysis Plan Authors: [name]

Department of Epidemiology and Biostatistics, Zhejiang University

School of Medicine, China

E-mail: [contact]

1. Introduction

This trial is a multicenter, prospective, randomized, controlled, open label, parallel-group, non-inferiority trial to evaluate the safety and efficacy of stent-based diverting technique (SDT) versus ileostomy in rectal cancer patients. In this trial, SDT is considered to reduce the overall length of post-operation hospital stay and medical costs, improve patients' quality of life, while not increasing the peri-operative complication rate. The primary outcome was the 90-day incidence of severe complications (Clavien-Dindo grade \geq III). Secondary outcomes included overall complication rate, anastomotic leakage rate (grade B/C), length of postoperative hospital stay, hospitalization costs, and 90-day postoperative quality of life.

Patients were randomized 1:1 to two groups:

- SDT group: rectal cancer surgery plus stent-based diverting technique
- Ileostomy group: rectal cancer surgery plus protective ileostomy

Follow-up concluded 90 days after the last patient underwent surgery.

2. Population

● 2.1 Intent-to-treat population

The intent-to-treat (ITT) population will include all randomized participants, with grouping according to their originally assigned treatment,

regardless of whether the allocated intervention was actually received or completed. Primary and secondary outcome analyses will be performed in the intent-to-treat (ITT) population. As randomization was performed intraoperatively, a modified ITT (mITT) population was not defined in this study.

- **2.2 Per-protocol population**

The per-protocol (PP) population includes all randomized participants who completed the study as planned, with no major protocol violations, adequate adherence to the assigned intervention, and sufficient follow-up data for the primary outcome assessment. Primary and secondary outcome analyses will be conducted in the PP population as sensitivity analyses.

- **2.3 As-treated population**

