4.6 Primary outcome

The primary endpoint will be analyzed in the ITT population and defined as the rate of severe complications (Clavien-Dindo grade \geq III) within 90 days post-surgery, the primary endpoint will be assessed as follows (Time Frame: For the Study Group, from the SDT to 90 days after surgery; if the patient undergoes ileostomy as a salvage procedure, the time frame will be extended to 90 days after stoma reversal. For the Control Group, from ileostomy creation to 90 days after stoma reversal. For patients in

both groups who do not undergo stoma reversal, the time frame will be defined as 90 days after the initial surgery).

The primary non-inferiority analysis will be based on the risk difference (RD) with a predefined non-inferiority margin of 2.8%. The RD and its 97.5% one-sided confidence interval will be estimated using binomial regression with identity link. For the relative risk (RR), binomial regression with log link will be used to estimate the RR and two-sided 95% confidence interval. The RR is reported as a supplementary effect measure and will not be used for the non-inferiority test ((see appendix Table 2).

Non-inferiority margin justification: The non-inferiority margin of 2.8% was determined based on clinical relevance and pilot data. This margin was defined such that the severe complication rate in the SDT group would not exceed 120% of that in the ileostomy group (i.e., a 20% relative increase). Given the expected severe complication rate of 14% in the ileostomy group in our pilot study, the absolute non-inferiority margin was calculated as $14\% \times 0.2 = 2.8\%$. In clinical practice, an absolute increase of no more than 2.8% in severe complications is considered acceptable, as it is negligible compared with the substantial benefits of SDT: avoidance of stoma creation and reversal, shorter hospital stay, lower medical costs, and improved quality of life.

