4.7 Secondary outcomes

Secondary outcomes will be analyzed in the ITT population. Continuous variables (e.g., operation time, estimated blood loss, distance from anastomosis to anal verge, length of postoperative hospital stay, hospitalization cost, quality of life score) will be compared using the Student's t-test (for normally distributed data) or Wilcoxon rank-sum test (for non-normally distributed data), with the median difference and corresponding 95% confidence interval reported. For categorical variables (e.g., surgical approach, surgical type, anastomotic technique, overall/mild/severe complication rate, Clavien-Dindo grade), the two-

sided Pearson's χ^2 test or Fisher's exact test will be used as appropriate (see appendix Table 4).

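### Missing 90-day quality-of-life scores are dropped, and the per-protocol and as-treated sets offered as the check on missing data drop the same scores

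*SAP*

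**What the plan says.** All references are to SAP version 1.2.

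- **Outcome and set.** The Introduction lists "hospitalization costs, and 90-day postoperative quality of life" among the secondary outcomes. Section 2.1 defines ITT as everyone randomized and states: "Primary and secondary outcome analyses will be performed in the intent-to-treat (ITT) population".
- **Missing data (4.3).** "For missing baseline data (age, BMI, etc.), multiple imputation by chained equations (MICE) will be used". For quality of life, "only observed cases will be included in the analysis (missing values excluded from denominator"). No outcome is imputed.
- **Test (4.7, 4.2).** Continuous outcomes, quality of life included, "will be compared using the Student's t-test (for normally distributed data"), or otherwise by a rank-sum test. No covariates are named. The level comes from section 4.2: "Other comparisons will be two-sided at" 0.05. The appendix table headed Table 3 shows eight domain scores.
- **Check on missing data (4.8).** The per-protocol and as-treated analyses use the ITT methods. Comparing the three sets is meant to show, among other things, whether missing data influence the results.
- **Role of the outcome (4.6).** The accepted excess of severe complications is defended by the benefits of the stent technique: "avoidance of stoma creation and reversal, shorter hospital stay, lower medical costs, and improved quality of life".

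**The concern.** A patient-reported score can be missing because the patient is unwell, and patients with severe complications plausibly both score lower and return fewer questionnaires. If that link is stronger in one arm, the responders in that arm look healthier than the patients randomized to it, and an unadjusted comparison of responders carries the difference into the treatment effect.

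The plan has nothing that would reveal this. Section 4.3 imputes baseline variables, but the test in section 4.7 uses no covariates, so the imputed values do not enter the quality-of-life comparison. Section 4.8 offers a check that cannot do its job for this outcome. The stake is how far the trial's quality-of-life result can be trusted, and the SAP uses that benefit in arguing that its margin is clinically acceptable.

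**Working it through.** **1. Can section 4.8 detect the problem?** Take a randomized patient with no 90-day questionnaire.

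| Set | How it is formed | The missing score |
|---|---|---|
| ITT | all randomized, by assigned arm | omitted (4.3) |
| Per-protocol | no major violation, adherent, enough follow-up for the *primary* outcome | omitted if the patient is in the set; otherwise the patient is absent |
| As-treated | regrouped by treatment received | omitted |

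No set restores a score or models why it is missing. Agreement among the three says nothing about missing quality-of-life data.

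**2. The one stated figure near this point.** The margin is 0.14 × 0.20 = 0.028, or 2.8%, which reproduces. Quality of life does not enter it. The SAP gives no quality-of-life SD, expected effect, loss rate or sample size.

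**3. Size of the bias.** Let p be the share of an arm with severe complications, d the score deficit in those patients, and m1 and m0 the loss with and without a severe complication. Among responders the share with severe complications is

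q = p(1 − m1) / [p(1 − m1) + (1 − p)(1 − m0)]

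The observed mean is too high by d(p − q). The bias in the comparison is that quantity in one arm minus the other.

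From the SAP: p = 0.14 (ileostomy pilot rate, 4.6). Assumed: the same p in the stent arm, no true arm effect, m0 = 0.10, SD 20, 260 observed per arm.

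*Case A: d = 15, m1 = 50% in one arm and 20% in the other*
- q = 0.070/0.844 = 0.0829; inflation 15 × 0.0571 = 0.86
- q = 0.112/0.886 = 0.1264; inflation 15 × 0.0136 = 0.20
- Bias 0.65 points (from unrounded values) = 0.65/20 = 0.03 SD

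*Case B: d = 20, m1 = 60% and 10%*
- q = 0.056/0.830 = 0.0675; inflation 20 × 0.0725 = 1.45
- q = 0.126/0.900 = 0.14; inflation 0
- Bias 1.45 points = 1.45/20 = 0.07 SD

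The bias favours whichever arm loses more of its patients with complications: +0.65 and +1.45 towards the stent technique if that is the stent arm, −0.65 and −1.45 if it is the ileostomy arm.

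**4. Effect on the two-sided 5% test.** SE = 20 × √(2/260) = 1.75. The shifts are 0.65/1.75 = 0.37 and 1.45/1.75 = 0.83 standard errors, so a true null is rejected in about 6.6% and 13% of trials. Both percentages depend on the assumed number observed.

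**5. Second set of assumptions, in SD units.** With p = 14%, 5% loss elsewhere, 40% to 60% loss among one arm's patients with complications, and a deficit of 0.5 to 1.0 SD, the bias is 0.023 to 0.076 SD. Simulation with an assumed 500 per arm gave rejection of a true null in about 8% (deficit 0.8 SD, loss 40%) to 20% (1.0 SD, 60%). Estimating within arm and complication status, which is what an imputation model with those terms targets, left a bias of at most 0.003 SD, which is simulation noise.

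**6. When the bias is nil or very small.**
- Loss random, dependent on arm only, or equally dependent on complications in both arms with equal rates: 0.
- Same loss pattern (5% and 40%) but rates of 16.8% v 14%: 0.004 to 0.008 SD.

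**The case against.** **Size and direction are not in the SAP.** Only the 14% is documented, and only for the ileostomy arm. The loss rates, deficits, SD and sample size are assumptions, and even large differences in loss give a bias below a tenth of an SD. This stands, and it limits the point to one about an unchecked assumption.

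**A reader might infer that the analysis favours the stent technique.** The tempting argument is that contact differs by design, because ileostomy patients are followed to 90 days after reversal. That window, in section 4.6, belongs to the primary endpoint. The quality-of-life outcome is set at 90 days after surgery, and follow-up in the stent arm reaches that point. Open-label treatment makes unequal return possible; nothing in the SAP shows it or gives its direction.

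**A reader might infer that the margin or the non-inferiority conclusion depends on this outcome.** It does not. The margin is a fifth of 14%, and the primary test does not use quality of life, which is one of several items in the clinical argument for accepting the margin.

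**The plan limits loss in other ways.** Section 3.3 assigns retrieval of missing data, section 4.4 still asks for questionnaires after a post-surgery withdrawal, and section 4.2 requires the number analysed to be reported. These help, but none tests whether the remaining loss matters. Treating a patient who refuses further data as censored (4.4) has no clear meaning for a score compared by a t-test.

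**Replacing the test now would look post hoc.** Version 1.2 is marked final and describes follow-up in the past tense. Its imputation covers baseline variables only, so imputing outcomes is a new model. This is a fair reason to add an analysis and leave the prespecified one in place.

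**Conclusion.** The point holds as a gap in the sensitivity analyses. Quality of life is compared among responders without adjustment, and the sets that section 4.8 presents as the check on missing data cannot show whether missing scores matter. Where loss depends on complications and does so differently by arm, the illustrative bias is 0.03 to 0.07 SD in either direction; unequal complication rates alone give much less. The range rests on the assumed loss rates, deficits and SD, and the inflated error rates also on the assumed sample size. The documents do not establish that bias will occur or which arm it would favour. The consequence is confined to what can be concluded about a secondary outcome, though one that the SAP cites when it defends its margin. The change is worth making before the quality-of-life results are interpreted.

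**What to change.** Keep the observed-case analysis as prespecified and add the following.

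1. **Multiple imputation of the eight domain scores, separately by randomized arm.** Predictors: the Table 1 variables, worst Clavien-Dindo grade, leakage, stoma status and readmission, all tabulated in the appendix. Estimate the between-arm mean difference and pool it by Rubin's rules. Show the observed-case mean difference beside it, because the median difference in section 4.7 is not on the same scale.
2. **A delta shift on the imputed scores**, varied by arm and in both directions, to show how far missing scores would have to depart from missing-at-random to change the conclusion.
3. **Deaths.** Do not impute after death; report deaths by arm.
4. **Reporting.** Tabulate missing questionnaires by arm and complication status.
5. **Section 4.8.** State that this analysis, and not the per-protocol or as-treated comparison, is the check on missing quality-of-life data.

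The cost is a little more analysis work with a method that the SAP already names, although its use for an outcome is new. The imputation relies on missing-at-random given the listed predictors, which the delta shift probes. The analysis should be labelled as added after SAP version 1.2.

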4.4 Screening data

The CONSORT flow diagram will be used to summarize the progress of participants throughout the study. Participating sites are required to record details of all randomized participants, including those who no longer meet the eligibility criteria or do not undergo surgery. Protocol violations will also be summarized, along with the reasons for each deviation.

The number of participants who withdraw consent from the study will be summarized, along with the reasons for their withdrawal. For patients who withdraw prior to surgery, no further data submission will be required.

For those who withdraw after surgery, collection of treatment and follow-up data will still be required (including quality of life questionnaires). With patients' permission, data collected before withdrawal may still be used for analysis. If a patient explicitly states that they do not wish to contribute further data to the trial, their wishes will be respected, and the patient will be handled as a censored case.

4.5 Baseline characteristics

Baseline clinical data (including age, gender, body mass index, smoking status, alcohol consumption, etc.) documented in the baseline assessment form will be summarized separately for each treatment group, presented as means with standard deviations, and as counts and percentages. No statistical testing will be performed on these baseline variables (see appendix Table 1).

4.6 Primary outcome

The primary endpoint will be analyzed in the ITT population and defined as the rate of severe complications (Clavien-Dindo grade \geq III) within 90 days post-surgery, the primary endpoint will be assessed as follows (Time Frame: For the Study Group, from the SDT to 90 days after surgery; if the patient undergoes ileostomy as a salvage procedure, the time frame will be extended to 90 days after stoma reversal. For the Control Group, from ileostomy creation to 90 days after stoma reversal. For patients in

both groups who do not undergo stoma reversal, the time frame will be defined as 90 days after the initial surgery).

The primary non-inferiority analysis will be based on the risk difference (RD) with a predefined non-inferiority margin of 2.8%. The RD and its 97.5% one-sided confidence interval will be estimated using binomial regression with identity link. For the relative risk (RR), binomial regression with log link will be used to estimate the RR and two-sided 95% confidence interval. The RR is reported as a supplementary effect measure and will not be used for the non-inferiority test ((see appendix Table 2).

Non-inferiority margin justification: The non-inferiority margin of 2.8% was determined based on clinical relevance and pilot data. This margin was defined such that the severe complication rate in the SDT group would not exceed 120% of that in the ileostomy group (i.e., a 20% relative increase). Given the expected severe complication rate of 14% in the ileostomy group in our pilot study, the absolute non-inferiority margin was calculated as $14\% \times 0.2 = 2.8\%$. In clinical practice, an absolute increase of no more than 2.8% in severe complications is considered acceptable, as it is negligible compared with the substantial benefits of SDT: avoidance of stoma creation and reversal, shorter hospital stay, lower medical costs, and improved quality of life.

Subgroup analysis will be performed according to: Age (≥ 60 y or <60 y), Gender (female or male), Body mass index (≥ 24.0 or <24.0), Diabetes (Yes or No), Use of neoadjuvant radiotherapy (Yes or No), Tumor to anal verge (≥ 7 cm or <7 cm), Multiple high-risk factors (Yes or No), Pathological T stage (0-2 or 3-4), Pathological N stage (positive or negative), Presence of prior abdominal surgery (Yes or No), Center effect (High-volume centers ≥ 50 cases versus low-volume centers <50 cases) . For subgroup analyses, between-group differences and corresponding 97.5% CIs will also be presented. The RRs will be reported with corresponding 95% CIs (see appendix Table 3).

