The as-treated (AT) population comprises all randomized patients who actually received the intervention to which they were assigned, regardless of their original randomization group. In this trial, participants randomized to the SDT group but who ultimately underwent ileostomy for various reasons were included in the ileostomy group in the as-treated analysis, and vice versa. All as-treated analyses were conducted as sensitivity analyses.

- **2.4 Safety population**

The safety population comprises all randomized patients in this trial, except those who withdrew prior to surgery. Patients were categorized

based on the treatment actually received, on which safety monitoring was performed. As this is a surgical study with the primary outcome focused on perioperative complications, all eligible patients were included in the safety population. Adverse events were monitored and reviewed by the Data Safety and Monitoring Board (DSMB).

3. Data Management

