Number of high-risk factors, No. (%)		
Single	XX (XX)	XX (XX)
Multiple	XX (XX)	XX (XX)
Pathological TNM stage, No. (%)		
0	XX (XX)	XX (XX)
I	XX (XX)	XX (XX)
II	XX (XX)	XX (XX)
III	XX (XX)	XX (XX)

Table 2

Outcomes	Stent-based Diverting Technique (n=)	Ileostomy (n=)	P value
Primary outcome			
Events (severe complications), No	XX	XX	
Incidence of severe complications, % (95% CI)*	XX (95% CI, XX– XX)	XX (95% CI, XX– XX)	
Between-group difference in incidence, % (97.5% CI)	-XX (–∞, XX%)	-	XX
Relative ratio, % (95% CI)*	XX (XX–XX)	-	XX
Secondary outcomes			
Incidence of total complications, No. (%)*	XX (XX)	XX (XX)	XX
Incidence of mild complications, No. (%)*	XX (XX)	XX (XX)	XX
Complications (Events)	XX (XX)	XX (XX)	-
General complications, No. (%)	XX (XX)	XX (XX)	-
Anastomotic leakage (Grade B)	XX (XX)	XX (XX)	XX
Anastomotic leakage (Grade C)	XX (XX)	XX (XX)	XX
Anastomotic stenosis	XX (XX)	XX (XX)	XX
Intestinal obstruction	XX (XX)	XX (XX)	XX
Intestinal perforation	XX (XX)	XX (XX)	XX
Abdominal infection	XX (XX)	XX (XX)	XX
Bleeding	XX (XX)	XX (XX)	XX
Others†	XX (XX)	XX (XX)	XX
Stent or Tube-related complications, No. (%)	XX (XX)	XX (XX)	-
Stent displacement	XX (XX)	XX (XX)	-
Intestinal fistula‡	XX (XX)	XX (XX)	-
Mushroom-shaped tube-related dermatitis	XX (XX)	XX (XX)	-
Mushroom-shaped tube displacement	XX (XX)	XX (XX)	-
Stoma-related complications, No. (%)	XX (XX)	XX (XX)	-

Parastomal hernia	XX (XX)	XX (XX)	-
Dermatitis	XX (XX)	XX (XX)	-
Stoma obstruction	XX (XX)	XX (XX)	-
Stoma bleeding	XX (XX)	XX (XX)	-
Grade of complications			
I	XX (XX)	XX (XX)	XX
II	XX (XX)	XX (XX)	XX
III	XX (XX)	XX (XX)	XX
IV	XX (XX)	XX (XX)	XX
V§	XX (XX)	XX (XX)	XX
Converse to Stent-based Diverting Technique, No. (%)	-	XX (XX)	-
Converse to ileostomy, No. (%)	XX (XX)	-	-
Converse to salvage ileostomy, No. (%)	XX (XX)	-	-
Time of stent degradation			
No stent	XX (XX)	XX (XX)	-
Stent displacement	XX (XX)	XX (XX)	-
Before 3 weeks	XX (XX)	XX (XX)	-
3-4 weeks	XX (XX)	XX (XX)	-
5-6 weeks	XX (XX)	XX (XX)	-
Stoma ending, No. (%)#			
No stoma	XX (XX)	XX (XX)	-
Reversal on time (stage II)	XX (XX)	XX (XX)	-
Delayed reversal	XX (XX)	XX (XX)	-

Table 3

	Stent-based Diverting Technique	Ileostomy	P value
PHS and Costs	n=	n=	
Unplanned readmission, No. (%)	XX ± XX	XX ± XX	XX
PHS (stage I), days	XX ± XX	XX ± XX	XX
PHS (stage II), days	XX ± XX	XX ± XX	XX
PHS (Readmission),	XX ± XX	XX ± XX	XX
Total PHS, days*	XX ± XX	XX ± XX	XX
Total PHS (Only patients with reversal), days*	XX ± XX	XX ± XX	XX

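### Section 4.6 extends the SDT-arm window past reversal only for salvage ileostomy, so an SDT patient with a non-salvage ileostomy reversed later has no window that reaches the reversal

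*SAP*

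**What the plan says.** Section 4.6 sets the primary-endpoint window by four rules:

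- SDT arm, default: "For the Study Group, from the SDT to 90 days after surgery".
- SDT arm, extension: "if the patient undergoes ileostomy as a salvage procedure, the time frame will be extended to 90 days after stoma reversal".
- Ileostomy arm: "For the Control Group, from ileostomy creation to 90 days after stoma reversal".
- Patients in "both groups who do not undergo stoma reversal, the time frame will be defined as 90 days after the initial surgery".

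The SAP does not define 'salvage'. The Table 2 shell (Section 6) has two separate rows filled only in the SDT column: "Converse to ileostomy, No" and "Converse to salvage ileostomy, No".

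Sections 2.1 and 4.3 keep patients who switch treatment in their assigned arm for the primary ITT analysis. Section 2.3 moves them for the sensitivity analysis: "participants randomized to the SDT group but who ultimately underwent ileostomy for various reasons were included in the ileostomy group in the as-treated analysis". Section 4.8 says that the sensitivity models repeat the primary analysis. It does not say which window a moved patient takes.

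**The concern.** The extension depends on the label of the ileostomy and not on whether the patient has a stoma to be reversed. The SAP foresees SDT-assigned patients who receive an ileostomy that it does not class as salvage. Such a patient carries the same stoma as a control and may have the same second operation, but no rule takes the window to that operation. The default that remains also starts at the SDT, which has no date if none was done.

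The endpoint is tested for non-inferiority on the risk difference. An event missed only in the SDT arm lowers that arm's rate and moves the difference towards a non-inferiority conclusion. The trial is open label, and without a clear rule the analyst would have to choose a window for crossover patients whose assignment is known.

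The gap does not depend on whether the two arms should share one window in general. It remains if the sponsor keeps arm-specific windows.

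**Working it through.** **The plan's own figure.** Section 4.6 derives the margin as 20% of an expected 14% ileostomy-arm rate: 0.14 × 0.2 = 0.028, or 2.8 percentage points. This reproduces.

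**The rules applied to each type of patient.**

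| Patient | Rule that fits | End of window |
|---|---|---|
| SDT, never a stoma | SDT default | 90 days after surgery |
| SDT, salvage ileostomy, reversed | SDT extension | 90 days after reversal |
| SDT, non-salvage ileostomy, reversed | only the SDT default is left | 90 days after surgery |
| SDT, any ileostomy, not reversed | no-reversal clause | 90 days after initial surgery |
| Control, ileostomy reversed | control rule | 90 days after reversal |
| Control, ileostomy not reversed | no-reversal clause | 90 days after initial surgery |
| Control converted to SDT, no stoma | no-reversal clause | 90 days after initial surgery |

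The third row is the gap. The extension fails because the ileostomy is not salvage, the control rule because the patient is not a control, and the no-reversal clause because there was a reversal. The opposite crossover, in the last row, does have a rule that fits.

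**Size.** Let *c* be the share of the SDT arm with a non-salvage ileostomy reversed after day 90. Let *r* be the risk of a severe complication between day 90 and 90 days after reversal. The SAP gives neither, so both are assumed: *c* = 3–10%, *r* = 3–8%.

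- Upper bound on the understatement of the SDT rate: *c* × *r*.
- The endpoint counts patients, so those who already had an event add nothing. With a 14% earlier-event rate (the SAP's expected ileostomy-arm rate) and independence: *c* × *r* × (1 − 0.14).

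| *c* | *r* | *c* × *r*, points | share of 2.8 | × 0.86, points | share of 2.8 |
|---|---|---|---|---|---|
| 3% | 3% | 0.09 | 3% | 0.08 | 3% |
| 5% | 5% | 0.25 | 9% | 0.22 | 8% |
| 10% | 8% | 0.80 | 29% | 0.69 | 25% |

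The ITT risk difference (SDT minus ileostomy) moves by the same amount, because the control arm is unaffected.

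**The case against.** The strongest reply is that the text is ambiguous and excludes nothing in words. The closing clause of Section 4.6 sorts patients of both arms by whether they had a reversal, which suggests that anyone reversed takes the reversal-based window. A row label in a table shell does not define a window, and the protocol may define conversion and salvage. This stands in part: the defect is a gap under the literal text, not an express exclusion. It does not close the gap. Reading 'salvage' as any SDT-arm ileostomy would make one of the two Table 2 rows redundant, and Section 4.6 still states no extension for the other kind.

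Four stronger readings are tempting, and the SAP does not support them:

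- *All stoma and reversal complications of converted patients go uncounted.* Severe complications in the first 90 days after surgery count, including those of a reversal within that time. Only later events are at issue, and the SAP does not say when reversal takes place.
- *Conversion happens at the index operation.* This is a fair inference from randomization during surgery and the separate rows, but the SAP does not date the conversion.
- *Reversal harms appear in no planned safety count.* Section 2.4 groups safety patients "based on the treatment actually received, on which safety monitoring was performed", which says nothing about a window. Section 5 has serious adverse events analysed and regularly reviewed, with no 90-day limit placed on them.
- *Converted patients have a shorter window than the rest of the as-treated ileostomy group.* Section 4.8 could equally be read as giving them that group's window. The SAP is silent, so a bias there is not shown.

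It is also fair to object that the size is one assumption multiplied by another. For that reason it is given only as an upper bound.

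**Conclusion.** The point holds as a gap in the endpoint definition for one foreseen class of patient: SDT-assigned, non-salvage ileostomy, reversed after day 90. Under the literal rule, their severe complications after day 90 are missing from the ITT SDT rate, while those of control and salvage patients with a reversed stoma are counted. The direction in ITT is fixed: the omission can lower the SDT rate or leave it unchanged, but cannot raise it.

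The size is unknown. Under the assumed ranges it is at most about 0.09–0.80 points, or about 0.08–0.69 after removing patients with an earlier event. The upper-bound range is roughly 3–29% of the margin. The low end is small. The effect is nil if no such patient exists or if all are reversed early enough for the relevant events to fall within 90 days of surgery. The window for these patients in the as-treated analysis is unstated. The text should be corrected because the repair is simple and the omission favours the claim under test.

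**What to change.** In Section 4.6, replace the salvage condition with: *if the patient receives an ileostomy for any reason (conversion or salvage)*. Start the window at the index operation for every patient, so that it does not depend on an SDT that may not have been done. State that the same stoma-based window applies in the ITT, PP and AT analyses, which settles the as-treated question too.

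The cost is small. Post-day-90 complications must be retrieved for what are probably few converted patients. The table shells already provide SDT-arm cells for stoma outcome and for stage II stay and cost, and Section 3.3 makes each centre's data manager responsible for retrieving missing data. It is best done before database lock, since Section 3.4 bars edits to locked data. The SDT rate may come out slightly less favourable.
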